8. DOSE MODIFICATIONS & DELAYS

Not applicable.

9. ADVERSE EVENTS: REPORTING REQUIREMENTS

This study will also be monitored by internal oversight specialists at the University of Iowa. The Data and Safety Monitoring Plan of the Holden Comprehensive Cancer Center provides standard operating procedures to monitor all clinical cancer trials at the UIHC. All investigator-initiated trials are automatically monitored by the Data and Safety Monitoring Committee (DSMC). A detailed data and safety monitoring plan for this study is on file with the DSMC. This study has been assigned as a risk level 4 as an IND phase 2b/3 study

9.1. Determination of Reporting Requirements

The clinical research team is responsible for collecting and recording the research data. As these results are collected, all toxicities and adverse events will be identified and reported to the principal investigator (PI). The PI will determine final relationship of the event to the investigational products (⁶⁸Ga PSMA-HBED-CC):

- Grade 1 and 2 events do not require attributions assigned.
- Grade 3 and higher adverse events require attribution determination.
- All serious adverse events (SAEs) require attribution determination.

Toxicity will be graded according to NCI's Common Toxicity Criteria (CTCAE v4). The principal investigator will have final responsibility for determining the attribution of toxicity as it is related to the investigational product.

9.2. Institutional Review Board reporting requirements

Adverse events that meet criteria of both *serious* and *attributed* (possible, probable, or definite) to the study agent. Thus:

- Serious adverse events *and*
- Attributable to ⁶⁸Ga PSMA-HBED-CC

Report to the IRB *via* HawkIRB within 10 business days of event

9.3. FDA reporting requirements [[name], sponsor]

Adverse events that meet criteria of *serious*, *unexpected*, and *attributed* (possible, probable, or definite) to ⁶⁸Ga PSMA-HBED-CC must be reported to the sponsor or the sponsor's appointed designee:

- Only serious adverse events are reported to FDA[21 CFR 312.32]
- Attributable to 68Ga PSMA-HBED-CC with a causal relationship as described [21 CFR 312.32 (c)(1)(i)]
- Unexpected, as defined by the FDA: "...not listed in the investigator brochure or is not listed at the specificity or severity that has been observed; or, if an investigator or, if an investigator brochure is not required or available, is not consistent with the risk information described in the general investigational plan or elsewhere in the current application, as amended."

9.4. Routine Adverse Event Reporting Requirements to DSMC

For non-serious adverse events, documentation must begin at radiotracer injection and continue through 24 hours post injection.

Routine adverse events will be reported by submission of an adverse events log to the DSMC at the time of DSMC review.

9.5. Serious Adverse Event Reporting to DSMC

Serious adverse events occurring after ⁶⁸Ga PSMA-HBED-CC injection will require a notification to the DSMC within 1 business day of learning of the event. The SAE capture window will be from the administration of ⁶⁸Ga PSMA-HBED-CC through 24 hours after administration. Serious adverse events that occur after this window are reportable if they are deemed reasonably attributed to the investigational drug, ⁶⁸Ga PSMA-HBED-CC.

10. CLINICAL TRIAL MONITORING

Clinical trial monitoring will be conducted to ensure the rights and well-being of human subjects are protected, that the reported trial data are accurate, complete, and verifiable, and that the conduct of the trial is in compliance with the currently approved protocol and/or amendment, with good clinical practice (GCP), and with applicable regulatory requirement(s).

10.1. University of Iowa's Human Subjects Office

The University of Iowa's Human Subjects Office (HSO) provides five different types of monitoring visits (post-approval responsibilities review, post-approval monitoring and education visit, directed monitoring, department of defense sponsored research monitoring, student principal investigator review). The HSO also provides an IND educational visit combined with a post-approval responsibilities review.

- Monitoring is performed by the HSO from their roster of qualified individuals.
- Monitoring is on-site.
- An educational IND visit will be requested by the PI. This will be done after IRB approval. The IRB indicate if accrual can begin prior to this visit.
- For the educational IND visit, if subjects have been consented, all signed consent documents will be reviewed.
- For the educational IND visit, the principal investigator will be provided a copy of the report documenting the visit within 1 month.
- Monitoring plans are not study specific. The plans are maintained by the HSO and are available for public review on-line.

10.2. The Holden Comprehensive Cancer Center

The Holden Comprehensive Cancer Center (HCCC) will provide monitoring for this investigator-initiated trial in compliance with their overarching monitoring plan on file with the National Cancer Institute (NCI) as well as with the individual clinical monitoring plan on file for this trial. Specifically:

- Monitoring is performed by the HCCC from their roster of qualified individuals.
- Eligibility review is ongoing, through remote review from OnCore, the clinical trials software.

- Monitoring is on-site and begins with the accrual of the first subject and will be performed at least twice per year. Frequency is adjusted based on risk, reported SAEs, compliance, patient population, and accrual rate.
- A minimum of 25% of subjects will be monitored for the entire study.
- Items reviewed include: eligibility, consent document, compliance to protocol, SAE reporting per institutional and federal requirements, accuracy of data against primary source, and investigational drug documentation.
- The sponsor-investigator will be provided draft copies of the report within one month of the visit.
- Independent audits will be conducted by the HCCC to verify monitoring is being performed per the filed clinical monitoring plan. The audit procedures are documented in their Quality Assurance Management Plan on file with the NCI.

11. STUDY CALENDAR

	Screening ^a	Baseline	V1 - PSMA-HBED-CC PET/CT ^{b,c}		Follow-up	
			Injection	Scan	Immediate	Long-term
Karnofsky PS	X					
informed consent	X					
PSA		≤3 mo V1				X ^d
imaging pull		≤3 mo V1				X ^d
pathology pull	X	≤3 mo V1				X ^d
serial PSA pull	X ^e					
change in management ^f		≤10d V1			≤30d V1	6 months V1
⁶⁸ Ga PSMA-HBED-CC			5 mCi			
20 mg IV furosemide			X			
HR, BP, Temp			supine ^g	supine ^g		
voiding				X ^h		
Adverse event query ⁱ		X	X	X ⁱ		

a 30 days window before the ⁶⁸Ga PSMA-HBED-CC scans

b Scan will be clinically interpreted, and entered into the medical record.

c A 2nd ⁶⁸Ga PSMA-HBED-CC PET/CT imaging visit may occur, if medically indicated. The 2nd scan will be obtained identical to 1st scan.

d data from follow-up imaging, laboratory PSA levels, and pathology as ordered for standard of care or study purposes will be analyzed and mined for outcomes

e serial PSA documenting biochemical recurrence as defined by AUA and/or ASTRO (as appropriate)

f change in management forms completed by referring/treating physician at three timepoints: within 10 days prior to imaging, within 30 days post-imaging, and then approximately 6 months post-imaging

g HR, BP, temp performed with subject supine immediately before and after injection and post-imaging of the scan

h subject should void immediately prior to the scan.

i final adverse event assessment is done 1 to 3 days post-injection but no earlier than 24 hours post-injection

12. EFFICACY ASSESSMENTS

Determination of efficacy requires two primary assessments.

The first assessment is the clinical read of the ^{68}Ga -PSMA-HBED-CC PET/CT scan. Trained readers will identify lesions positive for prostate cancer disease, and based on these results, will categorize specifically defined anatomical regions of the subject (Table 12.2) as positive for disease by ^{68}Ga -PSMA-HBED-CC PET/CT. Criteria are described in Section 12.1 below.

The second assessment is the reference standard determination of disease positivity or negativity also performed on the same specifically defined anatomical regions (Table 12.2). The reference standard definitions are described below, and consist of a combination of pathological confirmation, conventional imaging follow-up evidence, and serial PSA measurements. Criteria are described in Section 12.2 below.

For purposes of endpoints, four major regions are identified for final analysis as defined in Table 12.1. Each region is divided into subregions as defined in Table 12.2. All primary data from ^{68}Ga -PSMA-HBED-CC PET interpretations, pathology results, and conventional imaging results, will be collected per the subregions defined below. The final region assignments and results will be derived from the subregion data as applicable.

Region	Description
1	Prostate Bed
2	Pelvis outside of prostate bed including lymph nodes
3	Extrapelvic soft tissue, lymph nodes and organ metastases (non-bone)
4	Bone metastases

Table 12-1. Major Analysis Regions

Region 2: Pelvis outside of prostate bed	Region 3: Extrapelvic soft tissue	Region 4: Bone metastases
Right obturator	Lung	Spine
Left obturator	Liver	Ribs
Right external iliac	Pancreas	Pelvis
Left external iliac	Spleen	Extremities
Right internal iliac	Intestine	Skull
Left internal iliac	Mesentary	Sternum
Other pelvic regions	Brain	Clavicle
	Other soft tissue	Other bone
	Abdominal nodes	
	Thoracic nodes	
	Other nodes	

Table 12-2. Subregion Classification

12.1. **^{68}Ga -PSMA-HBED-CC PET Results Definition**

Imaging interpretation ^{68}Ga -PSMA-HBED-CC PET:

Local Interpretations: PET images will initially be interpreted by a board certified nuclear medicine physician or a board-certified radiologist experienced in reading PET at the time of the imaging study at the institution that the study is being performed. These interpretations will not be used for evaluation of the primary endpoint.

Blinded Read Logistics: Imaging data will be de-identified. PET data will be interpreted by two different readers in a random order at separate reading sessions. Cross sectional imaging (CT or MRI) from the ^{68}Ga -PSMA-HBED-CC PET will be available for anatomic correlate. The blinded readers will be blinded to all other imaging results and all other clinical data.

Reader Positivity and Negativity Definition: Sub-regions defined in Table 12.2 will be graded for the presence of suspected disease on a two-point scale by each reader (0=Negative or 1=Positive). A region will be judged as positive if at least one lesion in this region is visually positive..

12.1.1. Criteria for visual interpretation:

Sub-regions of suspected disease will be graded on a two-point scale by each blinded reader (0=Negative or 1= Positive). A region will be judged as positive if at least one lesion in this region is visually positive.

12.1.1.1. Lymph nodes will be considered positive if the ^{68}Ga -PSMA-HBED-CC uptake is focal and greater than blood pool (adjacent or mediastinal blood pool).

- Lymph nodes will be classified further by region: pelvic, retroperitoneal, thoracic and other. Additionally, pelvic lymph nodes will be sub-classified according to their localization as follows: R/L obturator, R/L external iliac, R/L internal iliac and other (total of 7 subgroups). These pelvic sub-regions will be correlated with reference standard results in these sub-regions, however this sub-region data will not be directly used for evaluation of the primary or secondary endpoints, but for exploratory analysis.

12.1.1.2. Visceral lesions will be considered positive if the ^{68}Ga -PSMA-HBED-CC uptake is focal and greater than physiologic background activity of the involvement organ or anatomic site.

- Visceral lesions will be classified further by major organ: lung, liver, pancreas... as defined in Table 2. These sub-regions will be correlated with reference standard results in these sub-regions, however this sub-region data will not be directly used for evaluation of the primary or secondary endpoints, but for exploratory analysis.

12.1.1.3. Bone lesions will be considered positive if the ^{68}Ga -PSMA-

HBED-CC uptake is focal and greater than physiologic bone marrow.

- Bone lesions will be classified by further by region: spine, ribs, pelvis, extremities, skull, sternum, and clavicle, as Defined in Table 12.2. These sub-regions will be correlated with reference standard results in these sub-regions, however this sub-region data will not be directly used for evaluation of the primary or secondary endpoints, but for exploratory analysis.

12.1.1.4. Prostate bed and prostate lesions will be considered positive if the ⁶⁸Ga-PSMA-HBED-CC uptake is focal and greater than physiologic background activity of the involvement organ or anatomic site.

12.2. Reference standard definition:

12.2.1. Histopathology/Biopsy will be the primary determinate of tissue positivity and negativity for prostate cancer disease. Pathology date, organ, and location as well as any notes related to the pathology will be obtained from the subject chart. The anatomical region/sub-region the pathology occurred in will be assigned by the investigator team:

⁶⁸Ga-PSMA-HBED-CC positive findings are aimed to be confirmed by histopathology/biopsy if clinically feasible. Pathology performed 60 days before or after the ⁶⁸Ga-PSMA-HBED-CC PET will be available for correlation.

Histopathological procedures and biopsies will be performed as clinically indicated and as per institutional protocol.

12.2.1.1. Lymph Nodes, Visceral Lesions, and Bone Lesions positive for disease by pathology.

- Lesions with positive pathologic confirmation will be regarded as positive for disease. The regionality of the resected tissue will be assigned into respective regions and sub-regions as described above in Table 12.2.

12.2.1.2. Lymph Nodes and Visceral Lesions negative for disease by pathology.

- Tissue removed and negative for pathology are considered negative for prostate cancer disease, unless subsequent conventional imaging or ⁶⁸Ga-PSMA-HBED-CC PET imaging demonstrates that targeted tissue were not resected. In this case:

- i. Subjects can be rescanned with dedicated CT, MRI, or ⁶⁸Ga-PSMA-HBED-CC PET/CT to determine if the suspicious ⁶⁸Ga-PSMA-HBED-CC tissue was removed. If the tissue is confirmed as removed, this is considered negative for disease.

ii. If ^{68}Ga -PSMA-HBED-CC PET/CT positive tissue is still present, a needle biopsy can be pursued at the discretion of the treating physician. Images of the procedure will be reviewed to determine if the correct tissue was biopsied.

- If the ^{68}Ga -PSMA-HBED-CC PET/CT positive tissue was biopsied, a negative pathologic finding of the biopsied tissue is considered negative for disease.
- If the ^{68}Ga -PSMA-HBED-CC PET/CT positive tissue was biopsied, a positive pathologic finding of the biopsied tissue is considered positive for disease.
- If biopsy or re-biopsy is not performed, or the wrong tissue was biopsied, change in node size as measured by conventional imaging and as defined below will be the criteria by which disease status will be defined.

12.2.1.3. Bone lesions: Given the high rate of false negative biopsies for osseous metastases in subjects with prostate cancer, subjects with negative bone biopsies of ^{68}Ga -PSMA-HBED-CC PET positive lesions will be further evaluated:

- If pathology demonstrates an alternative diagnoses that is known to be ^{68}Ga -PSMA-HBED-CC positive (eg Renal Cell Carcinoma metastases, Paget's disease), then this will be considered negative for disease.
- If pathology is indeterminate, then follow-up imaging as described below will be performed as per clinical standards at the site.

12.2.1.4. Although not routinely performed during standard practice, immunohistochemical staining for PSMA of tumor specimens (primary and lymph node metastases) may be performed, although not required.

12.2.1.5. All regions not sampled for biopsy/histopathology will be designated as indeterminate for disease by pathology. Conventional imaging follow-up may be used in these cases to determine tissue status.

12.2.2. Follow-up Imaging will be used as a secondary assessment for prostate cancer in the event pathology information is not available:

All subjects will be tracked for follow-up conventional imaging between 3-12 months post ^{68}Ga -PSMA-HBED-CC (dedicated CT, MRI and/or bone scan) as per site standard of care. If no follow-up imaging has been performed within the 9 months following the ^{68}Ga -PSMA-HBED-CC scan, then the research study will pay for an additional follow-up CT scan to be performed

in the 9-12 month window post-⁶⁸Ga-PSMA-HBED-CC scan. Follow up imaging will only be performed on subjects that have positive ⁶⁸Ga-PSMA-HBED-CC findings because conventional imaging assessment for disease is primarily targeting suspicious lesions identified by ⁶⁸Ga-PSMA-HBED-CC PET/CT. Interpretation of follow-up imaging will be performed by local read. Preferably, the follow-up conventional imaging should be the same modality/modalities as the initial staging work-up to allow for reproducible and accurate comparisons. Conventional imaging standards as described below will be used to determine tissue positive for prostate cancer disease. Conventional imaging will not be used to determine negative prostate cancer disease regions due to its inherently low negative predictive value.

Tissue positive for prostate cancer disease based on follow-up imaging:

12.2.2.1. Lymph nodes will be assessed by change in size.

i. Positive for disease:

- a. -For subjects undergoing systemic treatment (alone or in combination with targeted treatment): If on post-treatment follow-up imaging within 3-12 months, visually suspicious lymph nodes seen on CT or MRI decrease by more than 30% in short axis diameter and PSA declines by more than 50%.
 - If PSA increases by more than 25% (PCWG3 definition of recurrence) on systemic therapy, then an increase in the size of lesion by more than 20% in the short axis diameter will be considered a positive for disease.
- b. In subjects with localized suspected lymph node(s) receiving targeted treatment without concomitant systemic treatment there are two ways to achieve positive for disease designation:
 - If the subject shows a decrease of PSA by greater than 50% after targeted treatment and the lymph node does not enlarge (change in size less than 20% in the short axis diameter or less than 3 mm increase in short axis diameter) [OR]
 - If on post-treatment follow-up imaging within 3-12 months, lymph nodes seen on CT or MRI decrease by more than 30% in short axis diameter (with a minimum of 3 mm in change in size)
- c. For untreated subjects: If on follow-up imaging within 3-12 months, lymph nodes seen on CT or MRI increase by more than 20% in short axis diameter (with a minimum of 3 mm in change in size).

ii. Negative for disease:

- Conventional Imaging follow-up will not be used for assessment of negativity for disease.

iii. Indeterminate for disease

- Regions with no lymph nodes determined to be positive by the conventional imaging criteria described above and without pathology will be designated regions indeterminate for prostate cancer disease.
- Subjects that have had neither pathology sampling, nor conventional imaging follow up will have all regions designated as indeterminate for disease by reference standard.

12.2.2.2. Visceral lesions (non-lymph node soft tissue or organ) and prostate bed and prostate lesions will be assessed by change in size.

i. Positive for disease:

- a. For subjects undergoing systemic treatment (alone or in combination with targeted treatment): If on post-treatment follow-up imaging within 3-12 months, visually conspicuous lesions seen on CT or MRI decrease by more than 30% in long axis diameter and PSA declines by more than 50%.
 - If PSA increases by more than 25% (PCWG3 definition of recurrence) on systemic therapy, then an increase in the size of lesion by more than 20% in the long axis diameter will be considered positive for disease.
- b. In subjects with localized suspected lesions(s) receiving targeted treatment without concomitant systemic treatment there are two ways to meet positive disease criteria:
 - If the subject demonstrates a decrease of PSA by greater than 50% after targeted treatment [*OR*]
 - If on post-treatment follow-up imaging within 3-12 months, lesions seen on CT or MRI decrease by more than 30% in long axis diameter (with a minimum of 3 mm in change in size)
- c. For untreated subjects: If on follow-up imaging within 3-12 months, lesions seen on CT or MRI increase by more than 20%

in long axis diameter (with a minimum of 3 mm in change in size).

ii. Negative for disease:

- Conventional Imaging follow up will not be used for assessment of negativity for disease

iii. Indeterminate for disease

- Regions with no visceral lesions determined to be positive by the conventional imaging criteria described above and without pathology will be designated as visceral regions indeterminate for prostate cancer disease.
- Prostate bed and prostate regions not determined to be positive by the conventional imaging criteria described above and without pathology will be designated as prostate regions indeterminate for prostate cancer disease.
- Subjects that have had neither pathology sampling, nor conventional imaging follow up will have all prostate and visceral regions designated as indeterminate for disease by reference standard.

12.2.2.3. Bone lesions will be considered:

i. Positive for disease on baseline assessment:

- Any positive sclerotic lesion on the CT portion of the ⁶⁸Ga-PSMA-HBED-CC PET or on a separate CT obtained \leq 30 days before or after the PET/CT.
- Focal uptake on the baseline bone scan performed within one month of ⁶⁸Ga-PSMA-HBED-CC PET.
- Any MRI lesion in bone read as positive on the initial MRI performed within one month of ⁶⁸Ga-PSMA-HBED-CC PET.

ii. Positive for disease on follow up:

- Any new positive sclerotic lesion on CT within 12 months of ⁶⁸Ga-PSMA-HBED-CC PET scan
- Any new MRI bone lesion within 12 months of ⁶⁸Ga-PSMA-HBED-CC PET scan
- Any new focal uptake in bone within 12 months of ⁶⁸Ga-PSMA-HBED-CC PET scan

- In subjects with localized suspected bone lesion(s) receiving targeted treatment without concomitant systemic treatment:
- If the subject demonstrates a decrease of PSA by greater than 50% after targeted treatment.

iii. Negative for disease:

- Conventional Imaging follow up will not be used for assessment of negativity for disease

iv. Indeterminate for disease:

- Regions with no bone lesions determined to be positive by the conventional imaging criteria described above and without pathology will be designated bone regions indeterminate for prostate cancer disease.

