3. SUBJECT SELECTION

3.1. Eligibility Criteria

- 3.1.1. Pathologically proven prostate adenocarcinoma.
- 3.1.2. Rising PSA after definitive therapy with prostatectomy or radiation therapy (external beam or brachytherapy).
 - If post-radical prostatectomy, PSA > 0.2 ng/mL measured > 6 weeks post-operatively and confirmatory persistent PSA greater than 0.2 ng/mL (AUA recommendation for biochemical recurrence).
 - If post-radiation therapy, PSA that is equal to, or greater than, a 2 mg/mL rise above PSA nadir (ASTRO recommendation for biochemical recurrence).
- 3.1.3. Not receiving any other investigational agents (i.e., unlabeled drugs or drugs under an IND for initial efficacy investigations).
- 3.1.4. No other malignancy within the past 2 years (skin basal cell or cutaneous superficial squamous cell carcinoma or superficial bladder cancer are exempt from this criterion).
- 3.1.5. Karnofsky performance status (KPS) ≥ 50 (ECOG/WHO 0, 1, or 2).
- 3.1.6. Ability to understand and willingness to provide informed consent.

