6. PATIENT ASSESSMENTS

6.1. Post-consent Baseline Data Collection

Post-consent, the following data should be collected

- 6.1.1. **Serial PSA.** Most recent serial PSA values defining biochemical recurrence (i.e., two PSA values meeting AUA or ASTRO recurrence criteria).
- 6.1.2. **PSA.** Baseline PSA levels within 3 months of ⁶⁸Ga PSMA-HBED-CC PET/CT should be obtained.
- 6.1.3. **Pathology.** Copy of original pathology report documenting Gleason score and date sample obtained. Also, obtain a copy of any pathology reports 3 months prior to the ⁶⁸Ga PSMA-HBED-CC PET/CT.
- 6.1.4. **Bone scan.** If a bone scan was performed within 3 months of ⁶⁸Ga PSMA-HBED-CC PET/CT, obtain a copy of the images and the report.
- 6.1.5. **MRI.** If an MRI was performed within 3 months of ⁶⁸Ga PSMA-HBED-CC PET/CT, obtain a copy of the images and the report.
- 6.1.6. **CT scan.** If a CT was performed within 3 months of ⁶⁸Ga PSMA-HBED-CC PET/CT, obtain a copy of the images and the report.
- 6.1.7. **Change in management.** A pre-imaging survey of planned clinical management will be performed \leq 10 days prior to ⁶⁸Ga PSMA-HBED-CC PET/CT imaging.

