- 13.3.4.3. **^{68}Ga PSMA-HBED-CC PET/CT negative for osseous lesion by internal blind reader**, and pathology (if available) positive for any osseous lesion, or, osseous lesion positive for disease by imaging as defined in Section 12.2.2.3. If this criteria is met, the subject is defined as false negative for osseous disease.
- 13.3.4.4. A subject is defined as false negative for disease by ^{68}Ga PSMA-HBED-CC PET/CT if the subject is negative for disease in all regions by ^{68}Ga PSMA-HBED-CC PET/CT, but positive for disease by pathology or follow-up imaging in any region.

13.3.5. **Non-evaluable definitions:**

- 13.3.5.1. Any region that does not have sufficient data to meet the criteria for definition of true positive region, true negative region, false positive region, or false negative region will be classified as non-evaluable.
- 13.3.5.2. Any region that does not have sufficient data to meet the

criteria for definition of true positive subject, true negative subject, false positive subject, or false negative subject will be classified as non-evaluable.

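### Positive tissue excised up to 60 days before PET can set the reference standard, so a negative scan is scored false negative on a specimen that says nothing about disease present at the scan

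*Combined protocol and SAP*

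**What the plan says.** Section 12.2.1 puts pathology first: "Histopathology/Biopsy will be the primary determinate of tissue positivity and negativity for prostate cancer disease". It sets the time window with "Pathology performed 60 days before or after the" PET scan.

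For positive results, 12.2.1.1 states "Lesions with positive pathologic confirmation will be regarded as positive for disease" and continues "The regionality of the resected tissue will be assigned into respective regions and sub-regions". It makes no distinction between a needle biopsy, which leaves the lesion in place, and an excision.

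The only text that asks whether tissue was taken out is 12.2.1.2, which concerns negative results in nodes and visceral lesions: "Tissue removed and negative for pathology are considered negative for prostate cancer disease, unless subsequent conventional imaging or" PSMA PET shows that the target was left behind.

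The scoring rules are in 13.3.4. A PET-negative subject is false negative for nodal disease if pathology is positive for any node (13.3.4.1). He is false negative overall if PET is negative in all regions "but positive for disease by pathology or follow-up imaging in any region" (13.3.4.4). Section 5.6 is narrower: false negatives come only from positive biopsies of PET-negative lesions that are present on conventional imaging.

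No criterion in 3.1 or 3.2 bars recent surgery. After prostatectomy, 3.1.2 asks for "PSA > 0.2 ng/mL measured > 6 weeks post-operatively and confirmatory persistent PSA greater than 0.2 ng/mL". Section 6.1.3 tells sites to "obtain a copy of any pathology reports 3 months prior to the" scan, so reports on pre-scan surgery will be in the data.

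**The concern.** Per-subject sensitivity should compare the scan with disease that was in the body when the scan was done. A needle biopsy taken shortly before PET meets that condition. A lesion excised completely before PET does not, because its pathology report describes tissue that the scan could not image. The rules treat the two alike.

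This bears on the primary endpoint because a PET-negative man has few routes to a positive reference. Section 12.2.2 confines follow-up imaging to PET-positive subjects, although 6.4.3 does not repeat that limit. Pathology and the baseline bone criteria of 12.2.2.3 are the main routes left. False negatives will therefore be few, and each will weigh heavily. Section 13.1 intends the estimate to help set the target sensitivity and power of a larger study, so an error would carry forward.

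**Working it through.** **1. Path through the rules.** Take a man with positive nodes excised 50 days before PET, no other positive tissue, and a scan read negative in all regions.

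- 12.2.1: day −50 lies inside the 60-day window.
- 12.2.1.1: the nodes are positive and are assigned to their region.
- 12.2.1.2: does not apply, because the pathology is positive.
- 13.3.4.1 and 13.3.4.4: false negative for nodal disease and for the subject.
- 5.6: on its natural reading, not a false negative, since an excised node is not a PET-negative lesion present on imaging. The two sections disagree.

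**2. The same man with nodal uptake on PET.**

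- Uptake in a different nodal region from the excised nodes: 13.3.3.2 scores a false positive for nodal disease. Under 13.3.3.7 that carries to the subject unless another region is true positive. This affects PPV.
- Uptake in the same region: 13.3.1.1 asks for positive pathology in the very node that PET called, so the excised node should not confirm it. A spurious true positive needs matching by major region. Section 12 bases the final analysis on four major regions, and 12.1.1.1 keeps the pelvic sub-regions out of the primary and secondary endpoints, so that practice is not ruled out.

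**3. Timing for the primary operation.** Six weeks is 42 days, so the earliest qualifying PSA is on day 43. The pathology window closes at day 60. The overlap is at most 60 − 43 = 17 days. A confirmatory PSA, consent and the pre-imaging survey (6.1.7) must also fit, so the usable span is shorter. A later salvage node excision is not tied to this overlap and could fall anywhere in the 60 days.

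**4. The plan's own precision figures.** Half-width = 1.96 × √(p(1 − p)/30). For p = 70, 75, 80, 85 and 90% this gives 16.40, 15.49, 14.31, 12.78 and 10.74 points. Section 13.1 states 16.4, 15.5, 14.3, 12.8 and 10.7, so all five reproduce. They assume that all 30 subjects are reference-positive.

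**5. Size of the effect.** Sensitivity is taken as TP/(TP + FN). The formula printed in 13.1 has FP in place of FN, which is a separate matter. The documents do not give the number k of affected subjects, so k = 1 to 3 is an assumption, as is a scored sensitivity of 80%. Removing k false negatives that rest only on pre-scan excisions gives (Wilson 95% intervals):

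| k | Scored 24/30 = 80.0% (62.7 to 90.5) | Scored 16/20 = 80.0% (58.4 to 91.9) |
|---|---|---|
| 1 | 24/29 = 82.8% (65.5 to 92.4) | 16/19 = 84.2% (62.4 to 94.5) |
| 2 | 24/28 = 85.7% (68.5 to 94.3) | 16/18 = 88.9% (67.2 to 96.9) |
| 3 | 24/27 = 88.9% (71.9 to 96.1) | 16/17 = 94.1% (73.0 to 99.0) |

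Each subject accounts for about 3 points with 30 reference-positive subjects and 4 to 5 points with 20. If matching were by major region and k of the 24 true positives were spurious, removing them would give 23/29 = 79.3%, 22/28 = 78.6% and 21/27 = 77.8%, or about 0.7 points each.

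**The case against.** The strongest reply is that 5.6 already limits false negatives to biopsied lesions visible on conventional imaging and calls this uncommon. If 5.6 governed, the case in step 1 would not arise. But 5.6 sets no timing, and 13.3.4 holds the definitions written for scoring. The reply shows that the two must be reconciled; it does not close the gap.

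Several other replies stand and limit the point:

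- A reader might infer that a negative scan in such a man is a correct negative, or a miss that PET could not have avoided. The documents do not support that. He is eligible because PSA remained above 0.2 ng/mL after surgery, so disease may be present and PET may have missed it. The excised specimen shows neither.
- A reader might also infer that removed tissue confirms unrelated uptake as true positive. The text of 13.3.1.1 to 13.3.1.3 is against this, because it requires pathology on that same node or lesion.
- The gap is an omission. Section 12.2.1 makes pathology in the window available for correlation; no sentence says outright that pre-scan excisions count.
- The prostate specimen itself is a weaker example than a positive node dissection, since 12.2.1.1 names nodes, visceral lesions and bone lesions, and 13.3.4.1 to 13.3.4.3 have no prostate category.
- This is a 30-patient pilot without significance testing. One subject moves the estimate by about 3 points, against a stated half-width of 14.3 points at 80%.

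**Conclusion.** The false-negative problem holds on the text. Followed as written, 12.2.1, 12.2.1.1 and 13.3.4 can place in the primary denominator, as a PET miss, a subject whose only reference evidence left the body before the scan. The false-positive route through 13.3.3.2 is a second effect, on PPV. The true-positive route is conditional on matching by major region.

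The size per subject is as shown in the working. The total cannot be derived, because the documents do not say how many men had an excision in the 60 days before PET. That number is probably small: the overlap for a primary prostatectomy is days 43 to 60 at most, and the subject must also be node-positive and PET-negative everywhere. Severity is minor to moderate; the documents do not support treating it as a defect that must hold up the study.

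**What to change.** Add to 12.2.1:

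> Positive pathology obtained before PET is used as reference standard only for a lesion that remained in situ at PET (e.g. needle biopsy); a lesion completely excised before PET does not make its region reference-positive.

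Then align 5.6 and 13.3.4 with this, so that one false-negative rule applies. State in 13.3.1 and 13.3.3 whether PET and pathology are matched by lesion, sub-region or major region. Settle the rule before reads are compared with the reference standard, so that results cannot steer individual cases.

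The rule needs little new data: 12.2.1 already records pathology date, organ, location and notes. Pre-PET needle biopsies stay valid, and so does pathology on a lesion that was incompletely removed and still present at the scan.

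The cost is that a few subjects lose their reference. They are mostly PET-negative men, for whom 12.2.2 provides no study follow-up imaging, so they cannot simply fall back on imaging. Without other evidence they become non-evaluable under 13.3.5 and leave the denominator. That raises the sensitivity estimate, and some of them may be real misses. Their number should therefore be reported, with sensitivity shown both with and without them.
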